# **Study Summary**

Study Design	Feasibility study involving mixed methodology including quantitative and qualitative components
Study Participants	Pregnant patients
Planned Size of Sample (if applicable)	180 patients split into three cohorts
Follow up duration (if applicable)	N/A
Planned Study Period	24 months: 2/6/2025 to 2/6/2027
Research Question/Aim(s)	To assess the feasibility and acceptability of conducting a randomised controlled trial (RCT) of hand-held point-of-care ultrasound versus standard ultrasound for routine antenatal care

# **Funding and Support in Kind**

FUNDER(S)	FINANCIAL AND NON-FINANCIAL SUPPORT	
Liverpool Women's Hospital are providing the	GIVEN	
salary of [name]. This study is otherwise	The salary of [name] contributes to her	
not funded.	providing time and PI activities	

Roles and Responsibilities of Study Management Committees/Groups & Individuals

This group have jointly designed the study and will have responsibility for study management and interpretation of findings. This group is independent from the sponsor and funders.

# **Patient and Public Involvement and Engagement**

[figure not shown]
Service users and staff members have been consulted about the study concept and ultrasound device. The device is currently in use for other purposes within the trust.

Key Words: POCUS, Antenatal fetal imaging, fetal biometry, obstetrics

# **Study Flow Chart**

ABBREV	BBREVIATIONS		
AC	Abdominal Circumference		
AE	Adverse Event		
AR	Adverse Reaction		
BPD	Biparietal Diameter		
CI	Chief Investigator		
CRF	Case Report Form		
cCTG	Computerised Cardiotocograph (Dawes-Redman analysis)		
EDF	End-diastolic flow		
EFW	Estimated Fetal Weight		
EPR	Electronic Patient Record		
FGR	Fetal Growth Restriction		
FL	Femur Length		
GCP	Good Clinical Practice		
НС	Head Circumference		
HHPUD	Hand-held portable ultrasound device		
HRA	Health Research Authority		
НТА	Health Technology Assessment		
ICF	Informed Consent Form		
ISF	Investigator Site File		
LWH	Liverpool Women's Hospital		
MAU	Maternity Assessment Unit		

NHS	National Health Service			
NICE	National Institute for Health and Care Excellence			
NIHR	National Institute for Health Research			
PI	Principal Investigator			
POCUS	Point of care ultrasound			
REC	Research Ethics Committee			
RFM	Reduced Fetal Movements			
SAE	Serious Adverse Event			
SFH	Symphysis-Fundal Height (measurement)			
SGA	Small for Gestational Age			
SSG	Study Steering Group			
SUM	Standard Ultrasound Machine			
UA (PI)	Umbilical Artery (Pulsatility Index)			
UoL	University of Liverpool			

# 1. INTRODUCTION

This protocol describes the RUFUS-AFI study and provides information about procedures for entering

participants, study procedures, safety reporting and governance requirements. Every care was taken in its drafting, but corrections or amendments may be necessary. These will be circulated to investigators in the Study following receipt of required approvals.

Queries relating to this Study should be referred, in the first instance, to the study PI, [name].

This study will adhere to the principles outlined in the UK Policy Framework for Health and Social Care Research. It will be conducted in compliance with the protocol, the Data Protection Act 2018 and the UK GDPR as amended from time to time and any successor legislation in the UK and any other directly applicable regulation relating to data protection and privacy as well as any other regulatory requirements as appropriate.

# 2. BACKGROUND

In 2021, the UK Government announced its goals to reduce stillbirth rates. (1) This led to the promotion of the Saving Babies' Lives Care Bundle (v2 at the time), a strategy by NHS England to provide a framework of assessment and management of pregnancies by risk factor, with the aim of reducing stillbirth. One of its five key interventions is risk assessment and surveillance for fetal growth restriction. (2) With the introduction of the Saving Babies' Lives Care Bundle v2 in the National Health Service (NHS), there has been an increase in the demand for antenatal ultrasound, (3) which leads to increased costs for trusts due to increased need for ultrasound machines and technicians. The total cost of implementation of the Saving Babies' Lives Care Bundle is estimated at around £27m, with ultrasound scans comprising around £9.8m of this. (3)

Three million obstetric ultrasounds are performed annually in the UK, (4) representing a significant and rising cost to the health service. Standard ultrasound imaging is currently the gold-standard for diagnosing common clinical complications such as fetal malpresentation, abnormal placentation, in-utero demise, growth disorders, and abnormalities in amniotic fluid volume. Standard ultrasound imaging requires a high-specification machine, the cost of which can be around £15 000-£60 000.(5) Specialised probes may increase the cost, as well as maintenance and software updates. Due to the complexity of these machines, suitably qualified sonographers are needed to operate them and perform the examinations. Training and retaining higher numbers of these professionals due to an increase in demand for ultrasound has associated costs.

Point-of-care ultrasound (POCUS) is an ultrasound examination performed by the clinician attending the patient that directly affects immediate management. Indications vary across specialties, but POCUS is most

commonly used in imaging-critical specialties where emergencies can be fast-paced. Obstetrics is one such specialty. POCUS has traditionally been provided through use of portable cart-based ultrasound machines, but recent developments in microtechnologies have brought about a new era of hand-held devices which fit into the clinician's pocket, increasing portability and availability.

Due to the compact design and diagnostic limitations, point-of-care ultrasound (POCUS) devices are often cheaper than a standard ultrasound, and examinations performed with them may be more time efficient as well.(6) These devices are small and allow for ultrasound imaging to be performed rapidly, increasing their utility for emergency scenarios. Due to their lower cost when compared with standard ultrasound machines, there is an interest in their potential to be used for focussed routine examinations in antenatal care, such as growth scans. Following the COVID-19 pandemic, the use of hand-held devices specifically as opposed to larger cart-based models is of additional interest because their compact design makes them easier to clean between patients, reducing the risk of cross-contamination.

Point-of-care ultrasound (POCUS) examinations have been shown to be faster to perform than standard ultrasound.(6) When used for focussed examinations, POCUS does not require years of specialist training. Vinayak et al. trained midwives intensively for five weeks to identify common pregnancy complications with accuracy of 99.63%.(7) Shah et al. devised a brief but reliable training programme to enable emergency physicians to perform third trimester POCUS examinations quickly and reliably. (8)

POCUS machines, if reliable and acceptable, could become a means of delivering focussed ultrasound in antenatal care for specific indications. Evidence by Knights et al. demonstrated that a policy of either facility-based ultrasound by sonographers or POCUS used by midwives was effective in reducing the incidence of undiagnosed breech presentations in labour and an improvement in short-term neonatal outcomes.(9) Some initial data report reliability and validity of these devices, but their quality is not explicitly examined in relation to varying patient characteristics (such as maternal body mass index, uterine fibroids, or diabetes, or fetal risks such as SGA).(10-14) There has not yet been a systematic approach to assessing these devices for use in high-risk patient groups in a routine antenatal care setting.

If it is reliable to utilise POCUS devices to conduct these antenatal ultrasounds, there is potential cost-saving for trusts as well as timesaving for service users attending antenatal appointments.

In this feasibility study, we aim to ascertain the acceptability and validity of POCUS in different patient groups.

#### 3. RATIONALE FOR CURRENT STUDY

Increasing demand for ultrasound-based fetal growth surveillance is driven by the growing body of evidence implicating fetal growth restriction (FGR) and small for gestational age (SGA) as common causes of stillbirth, and a significant policy-based push toward reducing stillbirth rates at a national scale.

Patients at higher risk of FGR are identified following a risk assessment based on maternal characteristics and previous pregnancy outcomes, and are invited to undergo ultrasound assessment of fetal growth at regular intervals throughout the pregnancy (usually three to four weeks apart)(15). A cohort of these patients have risk factors that can make ultrasound assessment more challenging, including increased maternal body mass index (BMI) and diabetes leading to excess of amniotic fluid. Around one in 20 women who give birth in the UK have diabetes in pregnancy, either pre-existing or developed during the pregnancy. (16) Patients with diabetes and diagnosed SGA fetuses are required to attend more frequent scan appointments to ensure the fetal growth and wellbeing remains satisfactory (every two weeks or more if FGR is suspected). (17) Point-of-care devices are attractive to NHS services as they are more affordable than standard ultrasound machines, however it is unclear at present whether this is acceptable and feasible to deliver with training and image quality.

Patients presenting to the Maternity Assessment Unit (MAU) at or after 26 weeks of gestation with concerns regarding reduced fetal movements (RFM) in pregnancy represent a group with evolving risk for FGR. These patients are routinely offered a computerised CTG (cCTG) and an ultrasound scan assessment of fetal wellbeing comprising biometry, amniotic fluid volume assessment, and umbilical artery doppler studies. In our hospital, patients presenting with RFM at 39 weeks of gestation or greater are offered delivery via induction of labour or caesarean section and will only undergo ultrasound assessment in the event they decline delivery. As such, patients at 39 weeks or greater presenting with RFM will not be approached for this study.

Pilot and feasibility studies are not limited to trials or interventional research. The aim of this study is as a preliminary assessment of the feasibility and acceptability of the Vscan for different indications across different groups. We aim to explore practical aspects such as the potential for wide-scale implementation and engagement from patients. This study will provide a guide to the design of future studies and will provide information about appropriate statistical methodologies for the development of an intervention or full-scale

study.

#### 4. THEORECTICAL FRAMEWORK

We have designed the RUFUS-AFI study in accordance with the CONSORT 2010 Statement: Extension to Randomised Pilot and Feasibility Trials (18). This guideline provides a structured framework for reporting feasibility studies, and outcomes for the study will be reported in line with the recommendations.

# 5. RESEARCH QUESTION/AIM(S)

To assess the feasibility and acceptability of conducting a randomised controlled trial (RCT) of hand-held point-of-care ultrasound versus standard ultrasound for routine antenatal care

# 5.1. Objectives

Feasibility objectives:

- 1) To determine if an RCT to assess the reliability of hand-held point-of-care ultrasound assessments in highrisk pregnancy groups is feasible
- 2) To determine the acceptability of hand-held POCUS to patients
- 3) To determine if the outcome measures are suitable to assess reliability and acceptability
- 4) To determine if it is possible to remain blinded to measurements while conducting the study activity

# **Exploratory Objectives:**

- 1) To evaluate the intraclass correlation (reliability) of hand-held POCUS for the assessment of second and third trimester fetal biometry
- 2) To assess the validity of hand-held POCUS in patients with different antenatal risk factors (SGA, Diabetes, and RFM)
- 3) To examine the efficiency of hand-held POCUS for second and third trimester assessment of fetal biometry
- 4) To determine the minimum sufficient sample size to detect a difference in measurements taken with

#### **POCUS versus SUM**

#### 5.2. Outcome

The primary outcomes will be the acceptability and feasibility of point-of-care ultrasound to patients. This will be assessed as:

- 1) The number of patients approached who agree to participate (objective 1)
- 2) The response rate to the questionnaire (objectives 2 and 3)
- 3) The number of patients willing to undergo POCUS scans in the future as determined by the questionnaire responses (objective 2)
- 4) The number of unblinding episodes that occur (objective 4)

The exploratory outcomes will investigate the reliability and validity of the point-of-care ultrasound device. This will be assessed as:

- 1) For categorical data, Kappa coefficients demonstrating 90% agreement or greater (objectives 1 and 2)
- 2) For numerical data, ICC 0.9 or greater (objectives 1 and 2)
- 3) For continuous data (fetal biometric measurements), high level of agreement with Bland Altman, defined as ≥95% of the differences between the two measurement methods fall within the clinically acceptable range of ±3 to ±7 mm, depending on gestational age (objectives 1 and 2)
- 4) The difference in the mean time taken to perform each type of scan (POCUS and SUM) (objective 3)
- 5) The number of patients in whom fetal assessment could not be performed (objective 2)
- 6) Data from the feasibility study will inform the sample size calculation for the full randomized controlled trial by providing estimates of outcome variability, effect size, and recruitment parameters necessary for a power analysis (objective 4)

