#### 8.2 Recruitment

### 8.2.1 Sample identification

We will publicise the study with posters and leaflets in the clinical waiting areas and we will encourage clinical staff interacting with these patients to offer participation in the study. Potential articipants will be approached by the clinical care team about participation, and if interestd referred to the research team who also work in the clinical care team.

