#### 10. STATISTICS AND DATA ANALYSIS

### 10.1 Sampling

All pregnant patients attending Liverpool Women's Hospital Trust (diabetes antenatal clinic, fetal medicine unit growth clinic, maternity assessment unit with reduced fetal movements, admitted in antenatal ward with reduced fetal movements) will be considered to take part in this study.

As this is an exploratory study and no hypothesis testing is planned a formal sample size calculation has not been performed.

We will aim to include 60 patients per cohort. There will be three cohorts, so the total number of patients will be 180, and the number of scans performed 360. The sample size estimation was determined by the study team including the statistician because this is an exploratory study with a binary primary outcome (acceptable vs non-acceptable). A review of feasibility studies by Totton et al. (22) evaluated three studies of sample size estimations. The most recent of these studies was by Teare et al. (23), who recommend 60 participants per arm for feasibility studies with binary outcomes. 60 participants per cohort will generate sufficient results for feasibility and acceptability to achieve the proposed outcomes.

This sample size will also provide sufficient data for analysis of the secondary outcomes. As these are concerned with the level of agreement between the two ultrasound modalities, we will use Bland-Altman limits of agreement. Studies using this method rarely include sample size calculations, with an average sample size of 65.(24) The overall assessment of the devices from the combined three groups will involve a total sample of 180 paired scans.

Diabetes: The Diabetes antenatal clinic at LWH runs once a week on Tuesdays and sees between 20-40 patients per week. During a six-month period, this will equate to around 750 patients.

SGA: The Growth clinics at LWH run twice a week on Mondays and Thursdays and see roughly six patients per clinic. During a six-month period, this will equate to around 300 patients.

RFM: Patients present with RFM regularly to MAU at LWH. Around four patients per day will present. In a six-month period, this will equate to around 700 patients. The PI will aim to recruit from this clinical area weekly on Fridays.

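### Primary outcome 1 is a count with no recorded denominator, and no stated outcome measures willingness to be randomised, so feasibility objective 1 cannot be answered from the outcome mapped to it

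*Protocol*

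**What the plan says.** Feasibility objective 1 in section 5.1 is "To determine if an RCT to assess the reliability of hand-held point-of-care ultrasound assessments in highrisk pregnancy groups is feasible". Section 5.2 maps one primary outcome to it: "The number of patients approached who agree to participate (objective 1". The next outcome in the same list is written as a rate: "The response rate to the questionnaire (objectives 2 and 3". The third is again a number: "The number of patients willing to undergo POCUS scans in the future as determined by the questionnaire responses (objective 2".

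Section 10.1 sets the target: "We will aim to include 60 patients per cohort", and "There will be three cohorts, so the total number of patients will be 180, and the number of scans performed 360". It justifies 60 per cohort by a "binary primary outcome (acceptable vs non-acceptable" and a published rule of thumb of 60 per arm.

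On recruitment, section 8.2.1 says "Potential articipants will be approached by the clinical care team about participation, and if interestd referred to the research team", adding that the research team also works in the clinical team. Posters and leaflets in waiting areas advertise the study as well.

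The data sources named in section 10.1 are patient records, the scans and the participant questionnaires. Appendix 1 lists demographics and scan measurements. Neither mentions women who were approached and declined.

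Under section 6 every participant has both scans, standard care is unchanged, and the questionnaire covers perception of and satisfaction with the hand-held scan. Section 8.2.2 describes consent to an observational study with no effect on care. Exploratory outcome 6 in section 5.2 expects the data to supply recruitment parameters for the power analysis of the full RCT.

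**The concern.** Two separate questions decide whether the RCT is feasible: what fraction of eligible women would join, and whether they would accept random allocation to one modality. Outcome 1 as worded answers neither. A numerator that recruitment pushes towards a set target carries little information about uptake, and its denominator arises in a conversation for which the protocol names no record. Agreeing to an additional scan on top of usual care is also a smaller request than agreeing that chance may replace the standard scan with a hand-held one.

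At stake is the study's stated aim, and with it the recruitment parameters promised for the RCT. Refusals that are not logged when they happen cannot be recovered by later analysis, so this is not a detail that an analysis plan could supply afterwards.

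**Working it through.** **Reproducing the plan's figures.** 3 cohorts x 60 = 180 patients; 180 x 2 = 360 scans. Both agree with section 10.1. There is no power calculation to reproduce, because the protocol states that none was done.

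**What the count says about uptake.** Let D be the number of eligible women approached. Uptake is p = 180/D, with the Wilson 95% interval

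(p + z²/2D ± z√[p(1−p)/D + z²/4D²]) / (1 + z²/D), z = 1.96.

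The protocol gives no D, so the values below are assumptions chosen to show the range. The numerator is 180 in every row.

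| Approached (assumed) | Uptake | 95% CI |
|---|---|---|
| 200 | 90% | 85-93% |
| 300 | 60% | 54-65% |
| 600 | 30% | 27-34% |
| 900 | 20% | 18-23% |

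The same holds within a cohort: 60 agreeing is 75% of 80 approached or 25% of 240.

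**Can the clinic flows in section 10.1 stand in for D?** The six-month flows are about 750, 300 and 700. They follow from roughly 30, 12 and 28 patients a week over 25 weeks (30 x 25 = 750; 12 x 25 = 300; 28 x 25 = 700). Together they make 1,750, and 180/1,750 = 10.3% (8.9-11.8%). These are women passing through the clinics, not women approached. For reduced fetal movements, recruitment is planned for Fridays only; at four patients a day that is about 4 x 26 = 104 in six months, not 700. The flows are therefore not a usable denominator.

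**What if only referred women are counted?** Assume that 90% of women referred to the research team consent. Then 180/0.9 = 200 are referred and the apparent uptake is 90%. Uptake among all approached is 0.9 x the share that staff refer:

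- 20% referred: 0.9 x 0.2 = 18% (1,000 approached)
- 50% referred: 0.9 x 0.5 = 45% (400 approached)
- 80% referred: 0.9 x 0.8 = 72% (250 approached)

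Both inputs are assumptions; the point is the direction and possible size of the distortion.

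**Precision once D is recorded.** At p = 0.5 the half-width is 1.96√(0.25/D). Solving for D, a half-width of 5, 7 or 10 percentage points needs 385, 196 or 97 women approached. A useful estimate is within reach at the planned size.

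**Randomisation.** Set side by side, sections 5 and 6 give an aim about an RCT of hand-held versus standard ultrasound, and a design in which nobody is randomised and everybody has both. Of the four primary outcomes, the nearest to willingness to be randomised is outcome 3. It concerns having a hand-held scan in future, not having one instead of the standard scan by random allocation.

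**The case against.** Several points on the other side are sound.

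- A reader might infer that the result is fixed at 180 by design. The protocol does not support that: 180 is an aim, Appendix 3 places study close at 12 months, and the steering group reviews recruitment (section 11.5). A shortfall, a difference between cohorts, or the time to target would all be informative. This stands, and it limits the point to the case in which the target is met.
- Outcome 1 does mention patients approached, so it can be read as a proportion, and the example of questionnaire reporting in section 10.2 is a percentage. This softens the point, but the same list writes outcome 2 as a rate, and a proportion still needs a denominator that somebody records.
- A reader might infer that women who decline are lost to the data. That goes too far. The research team also works in the clinical team, Appendix 3 has a screening column, and the case report form and flow chart are not available. What can be said is that the protocol text names no approach or decline record.
- A reader might infer that nobody is asked about randomisation. The questionnaire is not shown, so this cannot be known. What can be said is that no stated objective, outcome or description covers it.
- A non-randomised feasibility study is a declared choice (section 3) and a legitimate one. The point is not that this study should randomise.
- A reader might infer that restricting outcome 3 to responders badly inflates acceptability. The protocol gives no response rate, and Appendix 3 puts the questionnaire at the scan visit, so the size of any such bias is unknown. Counting non-responders as unwilling would be one convention among several.

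**Conclusion.** The point holds in this form: objective 1 cannot be answered from the one primary outcome mapped to it. If the target is met, outcome 1 is 180 whether uptake is 90% or 20%; no record of the denominator is named; and no stated outcome measures acceptance of random allocation. The recruitment parameters promised under exploratory outcome 6 depend on the same missing denominator.

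The stronger statement, that the study can say nothing about feasibility, is not supported. Questionnaire response, unblinding episodes, failed assessments and scan time all bear on feasibility, although section 5.2 maps them to other objectives.

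The mismatch with section 10.1 is smaller. Acceptability is named as a primary outcome and outcome 3 is naturally yes or no, so what is missing is an explicit link to the binary outcome used to justify 60 per cohort.

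The uptake percentages rest on assumed numbers approached and illustrate the range; they do not predict this study's uptake. The conclusion does not depend on any one of them.

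**What to change.** 1. Redefine outcome 1 as women consented divided by eligible women approached, by cohort, with a 95% CI.
2. Add a one-line approach tally kept in each clinical area: date, cohort, agreed or declined, and reason if offered. Count poster and leaflet self-referrals separately, since they have no countable denominator.
3. Add one questionnaire item asking whether the woman would agree to be allocated at random to hand-held or standard ultrasound (if the existing form lacks it), list it as an outcome under objective 1, and report it as a proportion with a 95% CI.
4. State outcome 3 as a proportion of responders, with the number enrolled shown beside it, and name it in section 10.1 as the binary outcome on which 60 per cohort is based.

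The cost is a little clinic-staff time, one questionnaire item and a minor amendment. Sample size, scans and patient care are unaffected. The tally should be in place before recruitment starts, or at once if it has already begun.

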### 10.2 Data Analysis

### Data analysis and statistical analysis plan

Data arising from the questionnaires will be analysed in Microsoft Excel and will be reported using descriptive summary statistics, mean, medians, and counts (i.e. "54% of participants were satisfied with the POCUS scan").

Acceptability will be assessed using descriptive summary statistics, mean, medians, counts, and corresponding measures of variability.

Data will be analysed using SPSS (Statistical Package for the Social Sciences, IBM, Armonk NY).

The statistical methods have been chosen in collaboration with and at the advice of a University of Liverpool statistician ([name]) to ascertain agreement between the two methods of scanning (POCUS and SUM), and to enable appropriate statistical analysis of the proposed sample. Within each group we will use interclass correlation coefficients (ICC) and Spearman correlation coefficients (SCC) to check how closely the two methods agree by looking at the agreement between the paired measurements. Intraclass correlation coefficients measure how similar the measurements from the two methods are, indicating reliability or consistency for continuous variables. As the ICC approaches 1 (0.9 or greater), the greater the level of agreement. For this study, an ICC of 0.9 or greater will be considered a high level of agreement and indicate

increased reliability of the Vscan device.

To assess for difference in the scan duration, the mean scan time, median and interquartile ranges will be used. We will examine for correlation between the continuous variables of BMI and scan time with both POCUS and standard ultrasound. Calculation of a correlation coefficient will be performed with Spearman's correlation test.

Kappa coefficients measure agreement for categorical outcomes, such as assessments of fetal presentation or amniotic fluid levels. Values  $\leq 0$  indicate no agreement, 0.01–0.20 as none to slight, 0.21–0.40 as fair, 0.41–0.60 as moderate, 0.61–0.80 as substantial, and 0.81–1.00 as almost perfect agreement. These methods will be used to check for similarity within the methods (POCUS or SUM). This will ensure the measurements taken by the methods themselves are consistent.

Calculating the mean difference and 95% confidence intervals will provide estimate of any offset between two devices. Bland-Altman plots with limits of agreement will also provide a visual indication of the level of agreement between the two devices.

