# Measurements

POCUS: Fetal heartbeat, presentation, liquor volume (MVP), HC (mm), AC (mm), FL (mm), Umbilical Artery EDF, Placental location, EFW (g), Scan duration (HH:MM:SS)

SUM: Fetal heartbeat, presentation, liquor volume (MVP), HC (mm), AC (mm), FL (mm), Umbilical Artery EDF & PI, Placental location, EFW (g), Scan duration (HH:MM:SS

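### The categorical agreement criterion states kappa as a percentage, so its verdict depends on the reading, and kappa cannot score items that are constant on a device

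*Protocol*

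**What the plan says.** Protocol section 5.2 lists the criteria by which the reliability and validity of the hand-held device will be judged. For categorical findings the criterion is "For categorical data, Kappa coefficients demonstrating 90% agreement or greater (objectives 1 and 2"). The next item, for numerical findings, is "For numerical data, ICC 0.9 or greater (objectives 1 and 2").

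Section 10.2 gives the role of kappa: "Kappa coefficients measure agreement for categorical outcomes, such as assessments of fetal presentation or amniotic fluid levels". It then lists descriptive bands, ending with "0.61–0.80 as substantial, and 0.81–1.00 as almost perfect agreement". It has no cut at 0.90 and no percentage-agreement statistic, and it does not say how 90% maps to kappa.

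Section 14.1 (Measurements) lists what each device records. For the hand-held device the list begins "POCUS: Fetal heartbeat, presentation, liquor volume (MVP), HC (mm), AC (mm), FL (mm), Umbilical Artery EDF, Placental location, EFW (g"), and the standard machine has the same findings plus the umbilical artery pulsatility index. Heartbeat, presentation, umbilical artery end-diastolic flow and placental location are therefore recorded on both devices. On numbers, section 10.1 says "We will aim to include 60 patients per cohort", in three cohorts.

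**The concern.** Kappa measures how far observed agreement exceeds the agreement expected by chance from the margins. A kappa coefficient cannot show a percentage of agreement, so the sentence in section 5.2 joins two different quantities under one threshold. Anyone applying it must decide whether 90% refers to kappa or to the proportion of pairs that agree, and the same table can pass one and fail the other. If that decision is left until the data are seen, so is the verdict.

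There is a second difficulty even if kappa is clearly meant. Section 5.2 applies the criterion to categorical data without exception. Some of the recorded findings may hardly vary in this population, fetal heartbeat being the plainest example. Kappa carries little or no information for such items, and the protocol names no other rule for them.

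At stake is the categorical part of the device assessment. It is exploratory, but section 5.1 makes the suitability of the outcome measures a feasibility objective, and section 5.2 says the data will inform the full trial.

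**Working it through.** **The plan's own figure.** The 90% threshold is asserted, not derived, so there is nothing to reproduce. The related counts check: 3 × 60 = 180 pairs, and 180 × 2 = 360 scans.

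**Inputs.** Pairs per cohort: 60 (section 10.1). Threshold: 90% or 0.90 (section 5.2). Prevalence of the less common category: not given, so a range of 5% to 50% is assumed, plus the constant case. Each item is treated as two categories for simplicity.

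**Formula.** For a paired 2×2 table, kappa = (po − pe) / (1 − pe). Here po is the observed proportion of agreement and pe is the chance agreement from the margins. With equal margins at prevalence p, pe = p² + (1 − p)².

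**Step 1: 90% observed agreement on the kappa scale.** Take 6 discordant pairs, 3 each way, so po = 54/60 = 0.90. Cells are listed as both less common; hand-held only; standard only; both common. The last column is pe + 0.9 × (1 − pe).

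| Assumed prevalence | Cells | pe | kappa | Observed agreement needed for kappa 0.90 |
|---|---|---|---|---|
| 50% | 27, 3, 3, 27 | 0.500 | 0.400/0.500 = 0.80 | 95.0% |
| 20% | 9, 3, 3, 45 | 0.680 | 0.220/0.320 = 0.69 | 96.8% |
| 10% | 3, 3, 3, 51 | 0.820 | 0.080/0.180 = 0.44 | 98.2% |
| 5% | 0, 3, 3, 54 | 0.905 | −0.005/0.095 = −0.05 | 99.05% |

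Every row passes 90% observed agreement and fails kappa of at least 0.90.

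**Step 2: fewer discordant pairs.** With 2 discordant pairs (one each way), po = 58/60 = 0.967. Kappa is then 0.933 at 50% prevalence, which passes, but 0.896 at 20%, 0.815 at 10% and 0.649 at 5%, which fail. At 50% prevalence the readings part at 4 discordant pairs (po = 0.933, kappa = 0.867). The conflict therefore does not need a rare finding, though rarity widens it.

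**Step 3: constant items under the kappa reading.**
- All 60 pairs in one category on both devices: po = 1 and pe = 1, so kappa = 0/0, undefined. The same holds for all 180 pairs.
- One device constant, one discordant pair: po = 59/60 = 0.983 and pe = (60/60) × (59/60) = 0.983, so kappa = 0. With 180 pairs, po = pe = 179/180 = 0.994 and kappa is again 0. Pooling the cohorts does not help.
- One discordant pair each way and no concordant rare pair, n = 60: kappa = −0.017.

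**Step 4: raw agreement alone.** In the table 3, 3, 3, 51 observed agreement is exactly 90.0%, yet the hand-held device finds only 3 of the 6 less common cases (50%). It agrees on 51 of the 54 common ones (94.4%). A sole rule of 90% raw agreement would pass this table.

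**The case against.** The strongest reply is that the meaning is fairly clear. The named statistic is kappa, the next line puts the ICC threshold at 0.9 on the coefficient scale, and no raw-agreement statistic is named anywhere. On that reading the threshold is kappa of at least 0.90, and the table 3, 3, 3, 51 fails at 0.44. This largely stands. A reader might infer that the plan would pass a device missing half the less common cases, but that requires setting aside the word kappa. The text does not exclude that reading, but it is the less likely one.

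A reader might also take the bands in section 10.2 as a rival pass mark at 0.81. They are descriptive labels with no pass mark attached, and a target of 0.90 lies inside the top band ("and 0.81–1.00 as almost perfect agreement"), so there is no contradiction.

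Nor is kappa always zero or undefined for uncommon findings. With cells 2, 0, 1, 57 (hand-held misses 1 of 3), po = 0.983, pe = 0.920 and kappa = 0.79. If every rare case is concordant, kappa is 1. The firm statement is that kappa is undefined when both devices are constant and zero when only one is; short of that it can be unstable.

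Finally, section 10.2 gives presentation and amniotic fluid as its kappa examples, not heartbeat. Heartbeat comes within the rule because section 5.2 covers categorical data generally and section 14.1 records it on both devices. How to report a degenerate table could be left to an analysis plan. A threshold stated on the wrong scale cannot, because it is already fixed in the protocol.

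**Conclusion.** The point holds as a defect in a stated criterion. Section 5.2 expresses a chance-corrected coefficient as a percentage. At exactly 90% observed agreement in 60 pairs, kappa runs from 0.80 down to −0.05 over assumed prevalences of 50% to 5%, so the two readings give opposite verdicts. The likelier reading, kappa of at least 0.90, still cannot score perfect concordance on a constant item, and it gives 0 for a single disagreement when the other device is constant.

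These figures rest on assumed prevalences, two-category items and, in the table, an equal split of discordant pairs. The conflict appears at every prevalence tried.

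Severity is moderate to minor. A reader might infer that the study's main conclusions or its size are compromised. The documents do not support that: the primary outcomes are uptake, questionnaire response, willingness and unblinding; no hypothesis test is planned; and the 60 per cohort was not derived from kappa.

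**What to change.** Amend sections 5.2 and 10.2 as follows.

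1. State the threshold on the kappa scale, kappa of at least 0.90 with its 95% confidence interval, for items with real variation such as presentation and placental location. Name those items in advance.
2. For every categorical item, report observed agreement and the positive and negative agreement of the hand-held device against the standard machine, each with a 95% confidence interval, as separate quantities beside kappa.
3. For items with almost no variation, such as fetal heartbeat, replace the kappa criterion with the number of discordant pairs and positive and negative agreement. Say that any item found to be constant on either device is handled this way.
4. Do not substitute observed agreement of at least 90% as the sole criterion, for the reason shown in step 4 of the working.

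The cost is wording and some standard extra statistics; no new data are needed. The drawback is that positive agreement for rare findings will have wide intervals, since it rests on few cases (6 in the step 4 table).
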